6.0 Statistical Analysis

6.1 Software

The analysis will be conducted with R version 4.1.0.

6.2 Sample size

As of 21 July 2022, a total of 5,961 patients who initiated biologics are recorded in ISAR.

All patients (objective 3)

Preliminary numbers of patients that will enter the remission analysis (objective 3) are presented in Figure 2. While pre-biologic status for the asthma-related outcomes is not a pre-requisite for the description of remission status, patients with no pre-biologic data overall will be excluded from the analysis as an important part of the project will be to characterize the patients at biologic initiation.

[figure not shown]

Figure 2. Preliminary flowchart of data availability for patients who initiated any type of biologics as of 21 July 2022. Exclusions are sequential from top to bottom.

In patients impaired at biologic initiation, by single domains and composite definitions of response (objective 2)

Table 5. Preliminary sample size of impaired patients at biologic initiation (numbers presented are patients who were impaired at biologic initiation and with available data at follow-up).

Domains	N
1. Exacerbations(≥2 exacerbation in the year preceding biologic initiation)	1,392
2. Long-term OCS dose (receiving long-term OCS at biologic initiation)	475
3. Asthma symptoms control (uncontrolled or partially controlled at biologic initiation)	1,360
4. Lung function (FEV ₁ <80% predicted at biologic initiation)	1,179
1+2	313
1+2+3	264
1+2+3+4	134

6.3 Analysis for objective 1

Objective 1 aims at describing the study population used in objectives 2 and 3. To this end, the pre-biologic asthma-related outcomes will first be described individually and in composite variables. For individual asthma-related outcomes, both continuous and categorical variables will be used. The categories will be based on the eligible criteria used for impairment:

- Exacerbations: ≥2 versus <2
- Long-term OCS use: yes/no
- Asthma symptoms control: partly or uncontrolled versus well controlled
- Lung function: ≥80% versus <80% FEV1 predicted

The distributions will be compared between initiated biologic class using t-tests, Kruskall Wallis tests, or Person's Chi-squared tests as appropriate. The distribution of pre-biologic asthma related outcomes will also be compared between countries (or geographic regions in case of small sample size).

Patient characteristics (see Table 4) will also be described and compared univariately between the initiated biologic classes using appropriate statistical tests based on variable type and distribution.

6.4 Analysis for objective 2

Descriptive analysis

The proportion of patients responding to biologics as defined in section 5 will be computed overall and by biologic classes, for each individual domain and composite definition of response.

Patient characteristics will be described by levels of response using means, standard deviations, medians and interquartile ranges for continuous variables and numbers and percentages for categorical variables.

Trajectories from pre- to post-biologic status will also be described as cross-tabulations, by single domains and composite definitions.

Since the requirements for biologic initiation vary by countries, the above analysis will be stratified by pre-biologic status (eg, no exacerbation, no long-term OCS use, alone or in combination), overall and by country/geographic regions.

Association analysis (composite definitions)

Univariate analysis:

- The association between patient characteristics, including country/geographic region (see Table 4), and ordinal response levels will be tested by fitting ordinal logistic regressions using response levels as the outcome variable and each patient characteristic individually. Significance will be tested through log-likelihood ratios.
- Where the proportionality of odds assumption does not hold in the ordinal logistic regressions, binary logistic regressions will be used instead comparing extreme levels to all other levels of response.
- The comparisons will be performed overall and for each class of biologics separately.

• Multivariate analysis:

- We will use logistic regression techniques in a similar fashion as above, fitting
 in the same model the patient characteristics that are significant (p<.05) in the
 univariate analysis.
- o The models will be fitted overall and for each class of biologics separately.
- Optionally, a single model will be fitted adding biologic class in the model together with patient characteristics.

6.5 Analysis for objective 3

Descriptive analysis

The proportion of patients in different definitions of remission at follow-up as defined in section 5 will be computed overall and by biologic classes, for each individual domain and composite definition of response.

Patient characteristics will be described by definitions of remission using means, standard deviations, medians and interquartile ranges for continuous variables and numbers and percentages for categorical variables.

Trajectories from pre- to post-biologic status will also be described as cross-tabulations, by single domains and composite definitions.

Association analysis (composite definitions)

Univariate analysis:

- The association between patient characteristics, including country/geographic region (see Table 4), and different binary definitions of remission will be tested by fitting binary logistic regressions using remission yes/no as the outcome variable and each patient characteristic individually. Significance will be tested through log-likelihood ratios.
- The comparisons will be performed overall and for each class of biologics separately.

Multivariate analysis:

- We will use logistic regression techniques in a similar fashion as above, fitting
 in the same model the patient characteristics that are significant (p<.05) in the
 univariate analysis.
- The models will be fitted overall and for each class of biologics separately.
- Optionally, a single model will be fitted adding biologic class in the model together with patient characteristics.

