5.3 Analytical variables

Table 4. List of variables that will be used for the analysis.

Label	Type	Value	Construct/comments
Meta data ¹			
Calendar year at biologic	Numerical	-	
initiation			
Follow-up duration	Numerical	-	At least 24 weeks and as close as
(weeks)			possible to 1 year
Biologic therapy variables ¹			
Type of biologics	Nominal	Anti-IgE, anti-IL5/5R, anti-IL4/13, anti-TSLP	
Biologic therapy	Binary	0=Switched/stopped	Data indicating a discontinuation of initial
maintenance	,	1=Continue	biologic in the first year of follow-up
Asthma-related outcome v	ariables ²		
Exacerbation rates			
Exacerbation rate at	Discrete	-	Number of exacerbations in the year
biologic initiation			preceding biologic initiation.
Rate of exacerbations	Discrete	-	Number of exacerbations requiring
requiring hospitalisation			hospitalisation in the year preceding
at biologic initiation			biologic initiation.
Exacerbation rate at	Discrete	-	Number of exacerbations during the year
follow-up			following biologic initiation.
Rate of exacerbations	Discrete	-	Number of exacerbations requiring
requiring hospitalisation			hospitalisation during the year following
at follow-up			biologic initiation.
Reduction of ≥50% in	Categorical	Yes	N/A for patients <2 exacerbations in the
exacerbation rate	3	No	year preceding biologic initiation.
between baseline and		N/A	, , , , , ,
follow-up			
Long-term OCS use ²	'		
Long-term OCS dose at	Numerical	-	Prednisone-equivalent dosages.
biologic initiation (mg/day)			
Long-term OCS dose at	Numerical	_	Prednisone-equivalent dosages.
follow-up (mg/day)	Numerical		Treumsone-equivalent dosages.
Reduction of ≥50% in	Categorical	Yes	N/A for patients not receiving long-term
long-term OCS dose	Categorical	No	OCS at biologic initiation
between baseline and		N/A	OGG at biologic illitiation
follow-up		19/7	
Asthma symptoms control ²	2		 
Asthma symptoms Asthma symptoms	Ordinal	Well controlled	GINA 2020 classification (used by most
control assessment at	Jidillal	Partly controlled	participating centres). For centres
biologic initiation		Uncontrolled	reporting asthma symptoms control
biologic iriliation		Oricontrolled	
			assessment based on ACT (52) and/or
			ACQ (53), algorithms will be used to fit
			available data to GINA 2020 categories: - ACQ:
			0.75< Mean ACQ <1.5: Partly controlled Mean ACQ ≥1.5: Uncontrolled
			- ACT: Total ACT >19: Well controlled
			15< Total ACT ≤19: Partly controlled
			Total ACT ≤15: Uncontrolled

		1	

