Asthma symptoms	Ordinal	Well controlled	See above.
control assessment at		Partly controlled	
follow-up		Uncontrolled	
Improvement in asthma	Categorical	Yes	Yes:
symptoms control	22.29011001	No	Partially or uncontrolled → Well
between baseline and		N/A	controlled, or
follow-up		19/7	Uncontrolled → Partially controlled
ioliow-up			
			No: Remain uncontrolled or partially
			controlled
			N/A: Patients well controlled at baseline
Lung function ²			
Post-bronchodilator FEV ₁	Numerical	-	
at biologic initiation (mL)			
Post-bronchodilator FEV ₁	Numerical	_	
at follow-up (mL)	rtamonoai		
Post-bronchodilator FEV ₁	NI. una a mi a a l		
	Numerical	-	
percent predicted at			
biologic initiation			
Post-bronchodilator FEV ₁	Numerical	-	
percent predicted at			
follow-up			
Change in post-	Categorical	≥500mL increase	
bronchodilator FEV ₁	Janagariour	200 to 499mL increase	
between baseline and		100 to 199mL increase	
		Between 99mL	
follow-up			
		increase and 99mL	
		decrease	
		100 to 199mL decrease	
		≥200mL decrease	
Patient characteristics varia	ables		
Demographic characteristic			
Age at biologic initiation	Numerical	-	Attained age in complete years
(years)			/ mamou ago m complete yours
	Nominal	Female, male	
Sex			
Ethnicity	Nominal	Caucasian, South East	
		Caucasian, South East Asian, North East	
		Caucasian, South East Asian, North East Asian, African, Mixed,	
Ethnicity	Nominal	Caucasian, South East Asian, North East Asian, African, Mixed, Other, Unknown	
		Caucasian, South East Asian, North East Asian, African, Mixed, Other, Unknown Argentina, Australia,	
Ethnicity	Nominal	Caucasian, South East Asian, North East Asian, African, Mixed, Other, Unknown	
Ethnicity	Nominal	Caucasian, South East Asian, North East Asian, African, Mixed, Other, Unknown Argentina, Australia, Bulgaria, Canada,	
Ethnicity	Nominal	Caucasian, South East Asian, North East Asian, African, Mixed, Other, Unknown Argentina, Australia, Bulgaria, Canada, Colombia, Denmark,	
Ethnicity	Nominal	Caucasian, South East Asian, North East Asian, African, Mixed, Other, Unknown Argentina, Australia, Bulgaria, Canada, Colombia, Denmark, Greece, India, Ireland,	
Ethnicity	Nominal	Caucasian, South East Asian, North East Asian, African, Mixed, Other, Unknown Argentina, Australia, Bulgaria, Canada, Colombia, Denmark, Greece, India, Ireland, Italy, Japan, Kuwait,	

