Ethnicity Country Body mass index (BMI) at biologic initiation (kg/m²) Body mass index at biologic initiation in	Nominal Nominal	Caucasian, South East Asian, North East Asian, African, Mixed, Other, Unknown Argentina, Australia, Bulgaria, Canada, Colombia, Denmark, Greece, India, Ireland, Italy, Japan, Kuwait, Mexico, Poland, Portugal, Saudi Arabia, South Korea, Spain, Taiwan, UAE, UK, USA - Underweight Normal weight Overweight Obesity class I Obesity class II	Underweight: BMI<18.5 Normal weight: 18.5≤BMI<25 Overweight: 25≤BMI<30 Obesity class I: 30≤BMI<35 Obesity class II: 35≤BMI<40
Ethnicity Country Body mass index (BMI) at biologic initiation (kg/m²) Body mass index at biologic initiation in categories	Nominal Nominal Numerical Ordinal	Caucasian, South East Asian, North East Asian, African, Mixed, Other, Unknown Argentina, Australia, Bulgaria, Canada, Colombia, Denmark, Greece, India, Ireland, Italy, Japan, Kuwait, Mexico, Poland, Portugal, Saudi Arabia, South Korea, Spain, Taiwan, UAE, UK, USA - Underweight Normal weight Overweight Obesity class I Obesity class II Obesity class III	Underweight: BMI<18.5 Normal weight: 18.5≤BMI<25 Overweight: 25≤BMI<30 Obesity class I: 30≤BMI<35
Ethnicity Country Body mass index (BMI) at biologic initiation (kg/m²) Body mass index at biologic initiation in categories	Nominal Nominal	Caucasian, South East Asian, North East Asian, African, Mixed, Other, Unknown Argentina, Australia, Bulgaria, Canada, Colombia, Denmark, Greece, India, Ireland, Italy, Japan, Kuwait, Mexico, Poland, Portugal, Saudi Arabia, South Korea, Spain, Taiwan, UAE, UK, USA - Underweight Normal weight Overweight Obesity class I Obesity class II Obesity class III Current smoker, ex-	Underweight: BMI<18.5 Normal weight: 18.5≤BMI<25 Overweight: 25≤BMI<30 Obesity class I: 30≤BMI<35 Obesity class II: 35≤BMI<40

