Ethnicity Country Body mass index (BMI) at biologic initiation (kg/m²) Body mass index at biologic initiation in categories Smoking status at biologic initiation Asthma clinical features² Age of asthma onset	Nominal Nominal Numerical Ordinal	Caucasian, South East Asian, North East Asian, African, Mixed, Other, Unknown Argentina, Australia, Bulgaria, Canada, Colombia, Denmark, Greece, India, Ireland, Italy, Japan, Kuwait, Mexico, Poland, Portugal, Saudi Arabia, South Korea, Spain, Taiwan, UAE, UK, USA - Underweight Normal weight Overweight Obesity class II Obesity class III Current smoker, ex- smoker, never smoker	Underweight: BMI<18.5 Normal weight: 18.5≤BMI<25 Overweight: 25≤BMI<30 Obesity class I: 30≤BMI<35 Obesity class II: 35≤BMI<40 Obesity class III: BMI>40 Attained age in complete years at which
Ethnicity Country Body mass index (BMI) at biologic initiation (kg/m²) Body mass index at biologic initiation in categories Smoking status at biologic initiation Asthma clinical features²	Nominal Nominal Numerical Ordinal	Caucasian, South East Asian, North East Asian, African, Mixed, Other, Unknown Argentina, Australia, Bulgaria, Canada, Colombia, Denmark, Greece, India, Ireland, Italy, Japan, Kuwait, Mexico, Poland, Portugal, Saudi Arabia, South Korea, Spain, Taiwan, UAE, UK, USA - Underweight Normal weight Overweight Obesity class II Obesity class III Current smoker, ex- smoker, never smoker	Underweight: BMI<18.5 Normal weight: 18.5≤BMI<25 Overweight: 25≤BMI<30 Obesity class I: 30≤BMI<35 Obesity class II: 35≤BMI<40 Obesity class III: BMI>40 Attained age in complete years at which asthma was diagnosed or symptoms
Ethnicity Country Body mass index (BMI) at biologic initiation (kg/m²) Body mass index at biologic initiation in categories Smoking status at biologic initiation Asthma clinical features² Age of asthma onset (years)	Nominal Nominal Numerical Ordinal Numerical	Caucasian, South East Asian, North East Asian, African, Mixed, Other, Unknown Argentina, Australia, Bulgaria, Canada, Colombia, Denmark, Greece, India, Ireland, Italy, Japan, Kuwait, Mexico, Poland, Portugal, Saudi Arabia, South Korea, Spain, Taiwan, UAE, UK, USA - Underweight Normal weight Overweight Obesity class II Obesity class III Current smoker, ex- smoker, never smoker	Underweight: BMI<18.5 Normal weight: 18.5≤BMI<25 Overweight: 25≤BMI<30 Obesity class I: 30≤BMI<35 Obesity class II: 35≤BMI<40 Obesity class III: BMI>40 Attained age in complete years at which

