Ethnicity Country Body mass index (BMI) at biologic initiation (kg/m²) Body mass index at biologic initiation in categories Smoking status at biologic initiation Asthma clinical features² Age of asthma onset	Nominal Nominal Numerical Ordinal	Caucasian, South East Asian, North East Asian, African, Mixed, Other, Unknown Argentina, Australia, Bulgaria, Canada, Colombia, Denmark, Greece, India, Ireland, Italy, Japan, Kuwait, Mexico, Poland, Portugal, Saudi Arabia, South Korea, Spain, Taiwan, UAE, UK, USA - Underweight Normal weight Overweight Obesity class II Obesity class III Current smoker, ex- smoker, never smoker	Underweight: BMI<18.5 Normal weight: 18.5≤BMI<25 Overweight: 25≤BMI<30 Obesity class I: 30≤BMI<35 Obesity class II: 35≤BMI<40 Obesity class III: BMI>40 Attained age in complete years at which asthma was diagnosed or symptoms

Asthma duration	Numerical	-	Whole years between age of asthma onset and biologic initiation
Highest blood eosinophil count before biologic initiation (10 ⁹ cells/L)	Numerical	-	
Highest blood IgE count before biologic initiation (IU/mL)	Numerical	-	
Highest FeNO test before biologic initiation (ppb)	Numerical	-	
Allergy test results before biologic initiation	Binary	Positive, negative	From skin prick test or serum test for dust mite, grass mix, cat hair, mould mix, dog hair, aspergillus, weed mix, trees, food mix, animal mix, or other environmental allergens
Asthma-related medication	at biologic init	iation ²	1
Long-acting muscarinic antagonist (LAMA) in the year preceding biologic initiation	Binary	Yes, no	
Theophylline in the year preceding biologic initiation	Binary	Yes, no	
Leukotriene receptor antagonist (LTRA) in the year preceding biologic initiation	Binary	Yes, no	
Macrolide antibiotic in the year preceding biologic initiation	Binary	Yes, no	
Other steroid sparing agents in the year preceding biologic initiation	Binary	Yes, no	
Other treatment in the year preceding biologic initiation	Binary	Yes, no	
History of comorbidities at			
Allergic rhinitis ²	Binary	Yes, no	
Chronic rhinosinusitis ²	Binary	Yes, no	
Nasal polyps ² Eczema/atopic dermatitis ²	Binary Binary	Yes, no Yes, no	
Sleep apnea ³	Binary	Yes, no	
Anxiety/depression ³	Binary	Yes, no	
Osteoporosis ³	Binary	Yes, no	
Diabetes ³	Binary	Yes, no	
Chronic heart disease ³	Binary	Yes, no	
Pneumonia ³	Binary	Yes, no	
Peptic ulcer ³ Pulmonary embolism/ venous	Binary Binary	Yes, no Yes, no	
thromboembolism ³			
Cataract ³	Binary	Yes, no	

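### Sections 6.4 and 6.5 put every characteristic with univariate p<.05 into a model refitted on the same data, with no allowance for selection among 35 candidates, some of them redundant

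*Protocol*

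**What the plan says.** Protocol section 6.4 (objective 2) first tests "The association between patient characteristics, including country/geographic region (see Table 4), and ordinal response levels" one characteristic at a time. It then fits "in the same model the patient characteristics that are significant (p<.05) in the" univariate analysis. Section 6.5 repeats the rule for each binary definition of remission. In both sections, "The models will be fitted overall and for each class of biologics separately".

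The candidates come from section 5.3, headed "Table 4. List of variables that will be used for the analysis". Three of them are:
- "Age at biologic initiation", a number in years;
- age of asthma onset, which is "Attained age in complete years at which" asthma was diagnosed or symptoms began;
- asthma duration, defined as "Whole years between age of asthma onset and biologic initiation".

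BMI is listed as a number and again as "Body mass index at biologic initiation in categories".

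Table 5 in section 6.2 gives preliminary numbers for the three response composites: 313, 264 and 134. The protocol states no multiplicity control, no limit on model size, no covariates kept regardless of significance, and no shrinkage or validation.

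**The concern.** A variable that reaches the second model has already been chosen because it looked associated with the outcome in these patients. Refitting on the same patients and reading the new p-value at .05 ignores that choice. P-values come out too small, intervals too narrow, and retained effects tend to be exaggerated. Adjustment in the second step does little to undo this, because a null variable that passed by chance usually still looks significant beside one or two others.

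The aim in section 2.1 is to examine composite definitions in relation to patient characteristics and to find the most useful ones. That invites readers to compare predictor lists between definitions and classes. Under this rule the lists differ partly because the samples differ in size, and each coefficient is adjusted for a different set of variables.

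The redundant entries are a second, smaller defect. The rule says nothing about what to do if all three age terms pass, or if both forms of BMI pass.

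**Working it through.** There is no power or model-size calculation in the protocol to reproduce. Table 5 gives registry counts, and they are consistent with each other: 134 ≤ 264 ≤ 313 ≤ 475.

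**Candidates (Table 4).** Demographic 7 (age, sex, ethnicity, country, BMI, BMI category, smoking), asthma features 6, medications 6, comorbidities 16. Total 7 + 6 + 6 + 16 = 35.

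**Chance selections at one screen, all null and independent.**
- Expected number: 35 × .05 = 1.75.
- P(at least one) = 1 − .95^35 = 1 − .166 = 83.4%.
- P(at least two) = 52.8%.
- With 33 candidates, P(at least one) is 1 − .95^33 = 81.6%, so the exact count matters little.

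**Number of screens.** Take the overall population plus three classes, since anti-TSLP is not yet eligible.
- Objective 2: 3 composites × 4 × 35 = 420 tests, 21 expected false positives under a global null.
- Objective 3: 6 definitions × 4 × 35 = 840 tests, 42 expected.

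**Does the second step remove them?** Simulations of the screen and refit with no true effects and a binary outcome:

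| Setup | n | Mean selected | At least one p<.05 in the joint model |
|---|---|---|---|
| Mixed covariates, 5 regions, 25% events, 400 runs | 134 | 1.9 | about 70% |
| 35 independent normals, 35% events, repeated sets of runs | 134 | 1.8-2.0 | 76-77% |
| Same | 313 | 1.8-2.0 | 81-86% |
| Same | 1,000 | 1.8-2.0 | 83-88% |

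With 200-400 runs the Monte Carlo standard error is about 2-3 percentage points, for example √(.705 × .295/400) = .023. The rate does not fall as n grows. That is expected, because a .05 screen passes about 5% of null variables at any sample size.

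**Why the lists are not comparable.** Suppose a characteristic has the same true association in every composite, with expected z of 2.0 at n=134. This is an assumption for illustration. Expected z scales with √n, and the chance of passing is approximately P(Z > 1.96 − z).
- n=134: z = 2.00, passes 52% of the time.
- n=264: z = 2.0 × √(264/134) = 2.81, passes 80%.
- n=313: z = 2.0 × √(313/134) = 3.06, passes 86%.
- One third of 134 (assumed class size): z = 2.0/√3 = 1.15, passes 21%.

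Starting from z = 1.5 the four figures are 32%, 56%, 63% and 14%. Starting from z = 2.5 they are 70%, 94%, 97% and 30%. One unchanged association therefore enters some models and not others through sample size alone.

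**Redundant terms.** If duration = age − onset age exactly, an intercept plus the three terms has rank 3 out of 4. If duration is rounded down from dates, the variance inflation factor for duration is about 800-1,170 under assumed age distributions. All three must pass for this to arise. Simulated frequency was 0-0.03% with no effects and 1-24% with an assumed onset effect. Numerical BMI together with its categories gives a variance inflation factor of about 16 (assumed mean 28.5, SD 6), which is redundant but estimable.

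**The case against.** The strongest reply is that the study is exploratory and descriptive. Sections 6.4 and 6.5 provide descriptive tables by response level and remission definition, and cross-tabulations of pre- to post-biologic status. The characterisation does not rest on the multivariable models alone. This is right, and it limits what is at stake. It does not rescue the models themselves, whose p-values would still be read as adjusted associations.

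A second reply is that the false-positive figures assume no real predictors, while section 1.0 cites several, including blood eosinophils, FeNO, FEV1, prior hospitalisation and late onset. This also stands. A reader might infer that the reported predictors would be largely noise; the documents do not support that.

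Third, a reader might blame the 134 patients. The simulations show the rate is no lower with more patients. The 134 is also only one of nine composites, and the numbers for the six remission definitions are in a figure not shown. Nor has instability of a fitted model been demonstrated. About two terms pass by chance, and although the 35 candidates amount to about 65 parameters with 22 countries (about 48 with five regions), that is the pool and not the fitted model.

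Fourth, handling of collinearity and the choice of BMI form could be left to an analysis plan, and Table 4 also serves the descriptive tables. That is fair for BMI. But the screening rule is fixed in the protocol and, read literally, sends every passing entry into one model.

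**Conclusion.** The concern holds as a problem of selection and multiplicity. Under a global null with independent tests, 1.75 of 35 candidates pass by chance, and about 70-77% of analyses at n=134 report at least one false adjusted predictor, with no improvement at larger n. These percentages rest on assumed event rates of 25-35%, a binary outcome (the first-line model for response is ordinal) and no true effects. With real predictors present, the conclusion is that adjusted p-values and intervals are over-optimistic and that lists from different composites and classes cannot be compared.

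The redundancy point is conditional. A reader might infer that the model will fail outright; it becomes singular or nearly so only if age, onset age and duration all pass. The double entry of BMI is untidy rather than fatal.

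The change should be made before the models are run, but the descriptive results are not affected.

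**What to change.** In sections 6.4 and 6.5, replace the p<.05 screen with one of two options:
- A short covariate set chosen in advance on clinical grounds (section 1.0 names candidates), sized to the smallest composite and kept the same across definitions and classes. As a guide only, an assumed 10-20 patients per parameter gives 134/20 to 134/10, or about 7-13 parameters in the ordinal model. The binary fallback supports fewer: an extreme level of 10-30% (assumed) is 13-40 events, or about 1-4 parameters at 10 events each.
- A penalised ordinal or binary model on all candidates.

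Under either option, use at most two of age, onset age and duration, and one form of BMI. Report the univariate results as description. Label the multivariable results exploratory, including the by-class models in the 134-patient composite.

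The cost is protocol wording and modest programming in R, with no new data. With a fixed set, some characteristics are reported only descriptively. With penalisation, estimates are shrunken and lack simple p-values.
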